15.2.1 Adverse Events

Treatment emergent AEs will be summarized by system organ class, preferred term and ADA-status (positive, negative, boosted, unknown; each AE is classified according to the patients

ADA-status at the time of the AE occurrence;) displaying the number and percentage of patients with at least one AE recorded at each level of summarization. The total number of events and the number and percentage of patients with at least one TEAE will also be displayed. The summarization will be performed for the total safety analysis set and for the pivotal sub group. In addition, figures will be presented for each patient, displaying an overlay of drug exposure over time and adverse events marked out on the exposure curve. There will be two variants of this figure: one with dose by time, and the other with accumulated substance by time.

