3.1 Primary objective

The primary objective is:

- To assess the long-term safety and tolerability of SOBI003

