3.5 Study endpoints

3.5.1 Primary endpoint

The primary endpoint to evaluate the safety and tolerability of SOBI003 is:

- Treatment Emergent Adverse Events (TEAEs) and Serious Adverse Events (SAEs)

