5.2 Analyses and reporting

All final, planned, analyses identified in the protocol and in this SAP will be performed only after the last patient has completed the study.

Any post-hoc analyses included in the CSR, which were not identified in this SAP, will be clearly identified as such in the relevant section of the CSR.

For each patient in the study, all the associated safety and efficacy data in the SOBI003-001 study will be pooled and presented together with the SOBI003-002 study. Thus the SOBI003-001 study and the SOBI003-002 study are considered as a single, unified entity.

6 Estimands

There will be a de facto estimand in the study, which is the primary estimand for the evaluation of efficacy. The estimand is the change in

- cognitive decline in all the patients from the population captured by the inclusion and exclusion criteria (see Section 4.2.1 and Section 4.2.2) and the part of the NH population with a rapid progressive disease having a baseline age of 12 to 72 months, irrespectively of other medications used and adherence to treatment, and estimated by a repeated measures model of the change from baseline in DQ as described in Section 14.1.

- decline in HS levels in CSF in all the patients from the population captured by the inclusion and exclusion criteria (see Section 4.2.1 and Section 4.2.2) irrespectively of other medications used and adherence to treatment, and estimated by a repeated measures model of the change from baseline in HS as described in Section 14.1.

To address foreseeable inter-current events, such as drop-outs, all missing values will be imputed (see Section 14.1) in accordance with the treatment policy principle. A sensitivity analysis will be performed where no imputations are performed, but all values are used: If a patient has a missing value in any assessment, then the same patient's non-missing scores will be used in the repeated measures model. The repeated measures model (see Section 14.1) handles missing values based on the missing at random (MAR) assumption. One further sensitivity analysis for DQ will address this assumption based on zero imputations (see Section 14.1.1), the rationale being that the patients not assessed are those expected to have a severe DQ decline. Other sensitivity analyses for this purpose will be tipping point analyses, see Section 14.1.1.

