8.1 Safety analysis set

The Safety analysis set will consist of all patients in the study. For each patient in the study, all the associated safety and efficacy data in the SOBI003-001 study will be pooled and presented together with the SOBI003-002 study. The safety set will be used for the safety presentations.

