15.1 Drug exposure

The scope of the drug exposure will include the preceding FIH study as well as the present study. The presentations will be based both on the extension study separately, and pooled with the preceding study.

For each patient, graphs will be produced displaying dose by time and accumulated substance over time.

Duration of exposure will be calculated for each patient. It is defined as the total number of days a patient is exposed to study drug, and will be calculated using the following formula:

Time on treatment (days) = [(Treatment end date) – (Treatment start date) + 1].

The duration (days) and amount (mg) of exposure as well as the area under exposure curve will be summarized in a table using summary statistics, including the number of patients, the mean, standard deviation, median, minimum and maximum.

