15.2 Adverse events

An adverse event (AE) is defined as any untoward medical occurrence, including a clinically significant laboratory finding, symptom, or disease in a patient enrolled into this study regardless of its causal relationship to study drug.

A treatment-emergent AE (TEAE) is defined as any event not present before exposure to study drug or any event already present that worsens in either severity or frequency after start of treatment.

Adverse events will be coded using the latest version of Medical Dictionary for Regulatory Activities (MedDRA).

An overview table will present the following information.

- Number and percentage of patients reporting TEAEs
- Number and percentage of patients reporting serious TEAEs
- Number and percentage of patients reporting TEAEs leading to death
- Number and percentage of patients reporting TEAEs leading to study discontinuation
- Number and percentage of patients reporting TEAEs related to study drug

The number of events will also be displayed in this summary table.

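### The SAP tabulates TEAEs and SAEs only as pooled Weeks 1-104 counts, so adverse-event incidence in Weeks 25-104 cannot be read from the primary-endpoint tables

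*SAP*

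**What the plan says.** The primary objective is "To assess the long-term safety and tolerability of SOBI003" (SAP 3.1; Protocol 6.1), and the primary endpoint is TEAEs and SAEs (SAP 3.5.1).

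- **Pooling.** SAP 8.1 states for the safety set that "all the associated safety and efficacy data in the SOBI003-001 study will be pooled and presented together with the SOBI003-002 study". SAP 5.2 adds: "Thus the SOBI003-001 study and the SOBI003-002 study are considered as a single, unified entity".
- **TEAE clock.** SAP 15.2 counts "any event not present before exposure to study drug", plus worsening after the start of treatment. The clock starts at the first dose in SOBI003-001, not at Week 25.
- **Table layout.** The SOC/preferred-term table is described as "Treatment emergent AEs will be summarized by system organ class, preferred term and ADA-status", "displaying the number and percentage of patients with at least one AE recorded at each level of summarization". Total numbers of events are also shown there and in the overview, SAE, discontinuation, severity and relationship tables (SAP 15.2 to 15.2.5). None of these tables is split by study period or time on treatment.
- **Exposure.** SAP 15.1, by contrast, says: "The presentations will be based both on the extension study separately, and pooled with the preceding study". SAP 16.1 likewise plans PK on SOBI003-002 data alone and on both studies together.
- **Protocol.** Protocol 7.5.4.1.2 records AEs for this study from Week 25 to Day 8 of Week 104, including events since the last first-in-human visit. Protocol 9.4.7.1 tabulates AEs reported during the study by treatment dose level, among other factors. The SAP's AE tables carry over neither the period nor the dose-level split.

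**The concern.** The extension adds 80 weeks of treatment to the first 24. Its own safety question is what happens in those 80 weeks: whether events seen early continue, fade or are joined by new ones. Protocol 5.2 says that hypersensitivity and infusion reactions may still occur after the first 24 weeks, so change over time matters clinically. Protocol 7.1 also lets Cohort 1 children switch to a higher cohort's dose on entering the extension, so the two periods can differ in dose.

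A pooled table answers a different question: whether an event occurred at any time from first dose to Week 104. A child who had a given preferred term in Week 3 is already in the patient count, and recurrence in Week 90 does not change it. Recurrence does raise the event total, but that total is pooled too, so a reader cannot tell which part belongs to the extension. Nor is there an extension-only AE count to set against the extension-only exposure in SAP 15.1.

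**Working it through.** The plan states no figure here, so there is none to reproduce. The check concerns what the tables can identify.

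**1. Share of the window.** Weeks 1-24 are 24/104 = 23 % of the pooled period; Weeks 25-104 are 80/104 = 77 %.

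**2. Bounds without assumptions.** If a pooled row shows k patients with an event, the number with that event in Weeks 25-104 can be anything from 0 (all events early) to k (each of them also, or only, had one late). The same holds for a pooled total of E events: the extension share lies anywhere from 0 to E. ADA status at onset does not narrow this, because it is not a period.

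**3. Illustration.** Let p1 be the proportion of children with the event in Weeks 1-24 and p2 the proportion in Weeks 25-104. If the periods are independent, the pooled proportion is P = 1 - (1 - p1)(1 - p2). The values of p1 and p2 and the independence are assumptions; the documents give no AE rates. Nine children is the lower end of the planned 9-12.

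| p1 | p2 | P | Expected children of 9 |
|---|---|---|---|
| 0.90 | 0.10 | 1 - 0.10 × 0.90 = 0.91 | 8.2 |
| 0.90 | 0.60 | 1 - 0.10 × 0.40 = 0.96 | 8.6 |
| 0.30 | 0.10 | 1 - 0.70 × 0.90 = 0.37 | 3.3 |
| 0.30 | 0.60 | 1 - 0.70 × 0.40 = 0.72 | 6.5 |

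With an event common early, a sixfold difference in the later proportion moves the pooled count by less than half a child. With an event less common early, the same difference moves it by about three children, so masking in the patient percentages is partial.

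**4. What separate columns would rest on.** If all children stay on treatment and a year is taken as 52 weeks, 9 children give 9 × 24/52 = 4.2 patient-years in Weeks 1-24 and 9 × 80/52 = 13.8 in Weeks 25-104. For 12 children the figures are 5.5 and 18.5. Because the periods differ more than threefold in length, raw counts by period would mislead without a rate.

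**The case against.** The strongest defence is that the pooling is deliberate and legitimate. The extension follows the first study without a break, cumulative safety over 104 weeks is a fair meaning of long-term, and 77 % of that window is the extension. Timing is also available elsewhere. Per-patient figures mark AEs on the exposure curve (SAP 15.2.1), further figures plot AEs and titer against time (SAP 16.2), and all data are listed by patient (SAP 9). With 9-12 children a reader can count by hand.

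Much of this stands, and it rules out several stronger readings that a reader might infer:

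- *Long-term safety cannot be assessed from these tables.* Not supported: they give cumulative 104-week safety for children who entered the extension.
- *The tables ignore repeat events.* Not supported: event totals are planned throughout. Only their split by period is missing.
- *The any-TEAE row is saturated whatever happens after Week 24.* Not supported in general. Under an assumed constant, independent weekly probability of 2 % or 5 %, 1 - (1 - p)^24 gives 38 % or 71 % by Week 24. That would be the final pooled figure if nothing followed, against 88 % or 99.5 % by Week 104 if the rate continued. At 10 % per week the row is already at 92 % by Week 24, so the claim holds only for high early rates.
- *Only the Weeks 25-104 result can be the primary-endpoint result.* The SAP does not limit the endpoint to that period, so this is a preference.

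The defence does not supply a planned summary of the primary endpoint by period. Figures and listings allow one to be reconstructed, but no count or rate for the extension is specified. The pooled percentage is also conditional: entry requires completing the first study, so children who left before Week 24 are absent from the table.

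**Conclusion.** The point holds as a gap in presentation, not an error that invalidates the safety analysis. From the tables specified in SAP 15.2 to 15.2.5, the incidence of TEAEs and SAEs in Weeks 25-104 is not identified (anywhere from 0 to the pooled count), and a change after Week 24 cannot be seen. This follows from the table layout and needs no assumption. How much it hides does depend on assumed rates: a great deal for events common in the first 24 weeks (91 % v 96 %), much less for others (37 % v 72 %). The SAP already plans both views for exposure and PK, and the protocol's AE section defines the period from Week 25 and a dose-level split that the SAP drops. The change is worth making before database lock.

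**What to change.** Keep the pooled tables. In the overview, SOC/preferred-term and SAE tables of SAP 15.2 to 15.2.2, add one column for AE onset in Weeks 1-24 and one for onset from Week 25 to Week 104. Each should give number and percentage of patients, number of events, and events per patient-year, with denominators from the exposure summaries in SAP 15.1. Finer intervals, and the same split in the severity and relationship tables, are optional.

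State three rules with it: how an AE already ongoing at Week 25, or worsening after it, is assigned; how a partial onset date is assigned, since SAP 9.1 imputes only relative to first dose; and where SAEs reported in the 28 days after the last dose (Protocol 7.5.4.1.2) are shown.

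Reconcile the SAP's AE tables with the AE period in Protocol 7.5.4.1.2 and the dose-level split in Protocol 9.4.7.1, either by adding the split or by recording the departure with a reason. The period columns do not replace the dose split, because doses may also change within the extension.

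The cost is a few extra columns with small counts, many of them 0 or 1. No new data are needed: onset dates and infusion times are already part of the plan.

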15.2.2 Serious adverse events

A serious adverse event (SAE) is defined as any event that:

- Results in death.
- Is life-threatening (i.e., at immediate risk of death).
- Requires in-patient hospitalization or prolongation of existing hospitalization.
- Results in persistent or significant disability/incapacity.
- Is a congenital anomaly/birth defect (i.e., in an offspring to the study patient).

SAEs will be summarized by system organ class and preferred term displaying the number and percentage of patients with at least one SAE recorded at each level of summarization. The total number of events and number and percentage of patients with at least one treatment emergent SAE will also be displayed.

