#### **6.1.1 Primary endpoint**

The primary endpoint to evaluate the safety and tolerability of SOBI003 is:

- Treatment Emergent Adverse Events (TEAEs) and Serious Adverse Events (SAEs)

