### **Serious adverse event (SAE)**

An AE that meets one or more of the following criteria/outcomes is classified as serious:

- Results in death.
- Is life-threatening (i.e., at immediate risk of death).
- Requires in-patient hospitalization or prolongation of existing hospitalization.
- Results in persistent or significant disability/incapacity.
- Is a congenital anomaly/birth defect (i.e., in an offspring to the study subject).

Other medically important AE that may not result in death, be life threatening, or require hospitalization may be considered serious when, based upon appropriate medical judgment, they may jeopardize the patient or subject or may require medical or surgical intervention to prevent one of the outcomes listed above. Examples of such events are intensive treatment in an emergency room or at home for allergic bronchospasm, blood dyscrasias or convulsions that do not result in hospitalization or development of dependency or abuse.

Serious also includes any other event that the investigator or company judges to be serious. Any suspected transmission of an infectious agent via IMP shall also be considered serious.

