### **Hospitalization**

Hospitalization includes transfers within a hospital (e.g. from the hospital ward to the intensive care unit) and also includes admissions less than 24 hours. The following situations are not considered hospitalizations (although other SAE criteria may still apply):

- Outpatient procedures / ambulatory care.
- Emergency department visits.

Hospitalization in the absence of an AE occurring during the study should not be considered an SAE. This includes:

- Hospitalization due to a pre-existing condition not associated with a worsening of the pre-existing condition.
- Protocol specified admission.
- Elective admission, e.g. due to cosmetic surgery.
- Pre-planned admission for a condition specified at Baseline for the patient.

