**Table 12**                      **Severity grade definitions according to NCI CTCAE (version 4.03)**

Grade I	Mild; asymptomatic or mild symptoms; clinical or diagnostic observations only; intervention not indicated
Grade II	Moderate; minimal, local or non-invasive intervention indicated; limiting age-appropriate instrumental Activities of Daily Living (ADL)

Grade III	Severe or medically significant but not immediately life-threatening; hospitalization or prolongation of hospitalization indicated; disabling; limiting self-care ADL
Grade IV	Life-threatening consequences; urgent intervention indicated

Note the distinction between the seriousness (serious/non-serious) and the intensity (severity) of an AE. **Severe** is a measure of intensity; thus, a **severe** reaction is not necessarily a **serious** reaction. For example, a headache may be severe in intensity, but would not be classified as serious unless it met one of the criteria for serious events listed above.

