15.2.4 Adverse Events by Severity

Treatment emergent AEs will be summarized by system organ class, preferred term and severity (mild, moderate, severe). The summarization will be performed for the total safety analysis set and for the pivotal sub group. The table will display the number and percentage of patients with at least one TEAE recorded at each level of summarization within the preferred term. The total number of events along with the number and percentage of patients with at least one treatment emergent AE will also be displayed by severity. In the event of missing severity information, the severity will be displayed as 'Missing'.

The same presentation will be displayed for treatment emergent SAEs.

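### SAP 15.2.2 defines SAEs more narrowly than the protocol, and SAP 15.2.4 leaves Grade IV events without a defined severity row

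*SAP*

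**What the plan says.** **Endpoint.** Protocol 6.1.1 and SAP 3.5.1 name the same primary endpoint in the same words: TEAEs and SAEs.

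**Seriousness.** Protocol 7.5.4.1.1 lists five outcome criteria: death, threat to life, hospitalization or its prolongation, disability, and congenital anomaly. It then goes further:

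- "Other medically important AE that may not result in death, be life threatening, or require hospitalization may be considered serious when" medical judgement finds that they endanger the patient or need intervention to avert one of the listed outcomes.
- "Serious also includes any other event that the investigator or company judges to be serious".
- A suspected spread of infection through the study product is also serious.

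SAP 15.2.2 begins "A serious adverse event (SAE) is defined as any event that", gives the same five outcomes and ends there. It does not refer to the protocol for the rest.

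**Severity.** Protocol Table 12 grades events I to IV on CTCAE. Grade IV is "Life-threatening consequences; urgent intervention indicated". The wording of Grade III expressly excludes events that are an immediate threat to life. SAP 15.2.4 states: "Treatment emergent AEs will be summarized by system organ class, preferred term and severity (mild, moderate, severe". Its only other row is for missing severity.

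**The concern.** An SAP definition written as complete, but shorter than the protocol's, gives two possible answers to whether an event is an SAE. The difference matters here because one of the protocol's own examples of a medically important event is allergic bronchospasm treated intensively in an emergency room or in the home. The protocol's hospitalization rules put "Emergency department visits" among the situations that are not hospitalization, so such an event need not meet any of the five criteria that the SAP keeps.

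This is not a remote class of event for the product. Protocol 5.1.4 says an immune reaction may be expected, as with other enzyme replacement therapies. Section 5.2 warns of hypersensitivity, including anaphylaxis and delayed reactions after the patient has left hospital. Section 7.1 allows some infusions at home.

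The severity table has a related fault. The grade reserved for life-threatening events is collected, but the SAP says nothing about where it goes.

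**Working it through.** There is no stated figure to reproduce. The check compares the texts and then gives a scale.

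**Step 1. Seriousness criteria side by side**

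| Criterion | Protocol 7.5.4.1.1 | SAP 15.2.2 |
|---|---|---|
| Death | yes | yes |
| Immediate threat to life | yes | yes |
| Hospitalization or prolongation | yes | yes |
| Disability or incapacity | yes | yes |
| Congenital anomaly | yes | yes |
| Medically important | yes | no |
| Judged serious by investigator or company | yes | no |
| Suspected infection through the product | yes | no |

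**Step 2. The protocol's example under each text.** Take bronchospasm treated in an emergency room, with no admission, no immediate risk of death and no lasting disability. Under the protocol it can be serious as a medically important event. Under the SAP list it meets none of the five criteria, so it is not an SAE.

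**Step 3. Outputs that use the definition.** These are the serious-TEAE line of the overview (SAP 15.2), the SAE table (15.2.2), SAEs by severity (15.2.4) and SAEs by relationship (15.2.5).

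**Step 4. Severity levels side by side**

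| Protocol Table 12 | SAP 15.2.4 |
|---|---|
| Grade I, mild | mild |
| Grade II, moderate | moderate |
| Grade III, severe | severe |
| Grade IV, life-threatening | no row and no mapping rule |

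Pooling Grade IV with severe conflicts with how Table 12 words Grade III. Giving it no row leaves the table incomplete. Protocol 9.4.7.1 plans tables by maximum severity on CTCAE grading, so the SAP also departs from the protocol's planned analysis.

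**Step 5. Scale.** The protocol synopsis plans 9 to 12 patients. SAE incidence is the percentage of patients with at least one SAE, so leaving out one patient changes it by 100/n:

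- n = 9: 100/9 = 11.1 percentage points
- n = 12: 100/12 = 8.3 percentage points

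This applies only to a patient with no other SAE in the pooled SOBI003-001 and SOBI003-002 data.

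**Step 6. How likely is at least one such patient?** The documents give no rate. Let p be an assumed per-patient probability that the patient's only SAE rests on an omitted criterion, with patients independent. The chance of at least one such patient is 1 − (1 − p)^n. For example, with p = 5% and n = 9, it is 1 − 0.95^9 = 37%.

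| Assumed p | n = 9 | n = 12 |
|---|---|---|
| 2% | 17% | 22% |
| 5% | 37% | 46% |
| 10% | 61% | 72% |
| 20% | 87% | 93% |

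**The case against.** The strongest reply concerns how the data flow. Protocol 7.5.4.1.3 has the investigator settle seriousness, and 7.5.4.1.4 has SAEs reported on their own form. SAP 15.2.2 counts SAEs recorded, and it contains no algorithm that re-derives seriousness. The medically important criterion is also a matter of judgement ("Other medically important AE that may not result in death, be life threatening, or require hospitalization may be considered serious"), not something a programmer could apply. On this view the flag reaches the tables intact and the SAP list is only descriptive. This is plausible, and it makes the loss conditional. It does not remove the contradiction, because the SAP never says that the recorded flag governs. Nor can SAP 15.2 be assumed to mirror what is collected: 15.2.5 sorts causality from five levels, while the protocol collects only related or not related.

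Second, many acute reactions may still qualify through the hospitalization criterion. Transfers within a hospital and admissions under 24 hours count, and patients are normally admitted on infusion days. That stands. The exposed cases are mainly reactions outside hospital, and reactions managed within a planned stay that do not prolong it or meet another retained criterion. The documents do not say that reactions treated without admission are the ones most to be expected.

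Third, a reader might infer that the SAP has redefined the primary endpoint, or that key events go uncounted. The documents do not support either reading. The endpoint wording is identical and severity is not part of it. A medically important event remains a TEAE in the overview, in the table by system organ class and in the patient listings. A Grade IV event also stays in the TEAE counts, and if there is immediate risk of death it meets an SAE criterion that the SAP keeps.

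**Conclusion.** Both mismatches are in the current text and should be corrected. SAP 15.2.2 narrows the definition of one component of the primary endpoint by omitting three protocol criteria. SAP 15.2.4 has no defined place for a grade that the protocol collects.

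The effect on SAE reporting is conditional. If the SAP text governs, an event serious only through an omitted criterion is missing from the SAE outputs, and each patient with no other SAE lowers incidence by 8.3 points (n = 12) to 11.1 points (n = 9). If the recorded classification is used, nothing is lost. The documents do not settle which applies, so it would be too strong to say that the plan will under-report. How often such patients would occur is also unknown; the probabilities above rest on assumed rates.

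The severity fault is narrower: an undefined row in descriptive tables, not a lost event.

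**What to change.** - **SAP 15.2.2:** replace the five-item list with the full protocol 7.5.4.1.1 definition, including all three omitted criteria. State that the tables use the seriousness classification recorded by the investigator or sponsor.
- **SAP 15.2.4:** tabulate severity by Grades I to IV as collected under Table 12, for TEAEs and for treatment-emergent SAEs.

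No separate display of fatal events is needed. SAP 15.2 already has an overview line for TEAEs leading to death, and 15.2.6 provides a narrative for each death.

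The cost is two text edits before database lock and the matching table shells, with no new data and no change to the endpoint.
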